## 7.4 Table of Assessments

Visit	Screening/ Baseline	Randomisation	Treatment Visit 1	Visit 2 3 months ( $\pm 6$ weeks)	Visit 3 6 months ( $\pm 6$ weeks)	Visit 4 12 months ( $\pm 6$ weeks)	Visit 5  2 years ( $\pm 6$ weeks)	Visit 6 3 years ( $\pm 6$ weeks)	Visit 7 4 years ( $\pm 6$ weeks)	Visit 8 5 years ( $\pm 6$ weeks)	After Visit 8**
Informed consent	x										
Randomisation		x									
Fitness for surgery assessment	x										
PSA	x			x	x	x	x	x	x	x	x
Standard care referral pathway to regional uro-oncology centre	x										
MRI guided pre-op surgical planning			x								
RARP (standard/control or NeuroSAFE/intervention)			x								
Adverse events	x	x	x	x	x	x	x				
EQ-5D-5L – (P/C/E/T)*	x			x	x	x					
ICIQ – (P/C/E/T)*	x			x	x	x					
IIEF-5 – (P/C/E/T*)	x			x	x	x					
RAND36 – (P/C/E/T)*	x			x	x	x					
Additional Erectile Function (EF) questionnaire (P/C/E/T)*				x	x	x					
Additional Treatments Assessment				x	x	x	x	x	x	x	x
Health Resource Diaries data collection				x	x	x	x				
RAND36, IIEF, EQ-5D-5L, ICIQ and Additional EF questionnaire – (P/E/C/T)							x				
EPIC-26 questionnaire (P/E)*								x	x	x	x

\*P – Postal, E – Email, C – Clinic, T - telephone

\*\* after visit 8 data to be collected for a maximum frequency of annually

 Visits after 12 months dependent on future funding

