#### 10.1.2 Intervention Arm: NeuroSAFE RARP

NeuroSAFE RARP (intervention arm) will be performed in accordance with previously described methods, initially developed at the Martini Clinik, Hamburg, Germany. All patients in the NeuroSAFE arm will undergo initial bilateral NS where technically possible. The procedure differs from standard RARP in that initial insertion of the robotic camera port is through a modified incision using the Alexis Laparoscopic System (Applied Medical, Rancho Santa Margarita, CA).

Once the specimen is disconnected from its attachments, the specimen can be removed from the patient through the protected incision immediately.

Pneumoperitoneum can be re-established quickly by placing the laparoscopic cap back on the Alexis.

The specimen will then be painted by the operating surgeon (sites may differ, but at UCLH; yellow for left and green for right side of the prostate). The painted areas can be sprayed with a fixative spray if site prefers (to prevent ink running). The specimen will be delivered expediently to the pathology laboratory where frozen section analysis of the painted areas will be undertaken. Whilst this analysis is taking place the robot will be re-docked and pneumoperitoneum established. The robotic instruments will be reinserted. The surgeon will proceed to fashion the urethro-vesical anastomosis and perform a pelvic lymphadenectomy (where indicated) whilst the result of the frozen section analysis is awaited.

Upon delivery of the prostate gland to the pathology lab, a sharp blade will be used to remove the pre-painted surface of the gland (which had been in contact with the neurovascular bundles). The tissue sample will be snap frozen and embedded in OCT. Using a cryostat, 10-micron thick slices will be placed on slides. The entire length of the area of interest will be sampled in this way generating an average of 5 frozen sections per side and approximately 10 in total. The slides will be stained with H&E and will be examined by a consultant pathologist. As soon as examination is complete the pathologist will telephone the operating surgeon to give the result. On frozen section analysis, presence of cancer cells at the inked surface margin of the specimen constitutes a positive margin and the length of any positive surgical margin will be recorded.

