#### **Early post-operative**

Wound related problems; infection (2%), incisional hernia (2%)  
Thromboembolic event (deep vein thrombosis or pulmonary embolus 0.8%)  
Lymphoedema – 1% (higher incidence when eLND performed)  
Anaesthetic problems requiring admission to intensive care unit (2%)  
Gastrointestinal; ileus/damage to bowel requiring temporary colostomy (0.5%)  
Seroma – 1%  
Urethral Stricture – 2%

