### 13.7.2 Period of observation

For the purpose of this trial, the period of observation of serious adverse events extends from consent to 90 days post op as it unlikely any SAEs past this point will be related to surgery. This will reduce site reporting workload. Trial follow up should continue according to schedule once the SAE is resolved, if applicable. The trial will, however, continue to collect death SAEs throughout per section 13.7.1.

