3.1 Schedule of assessments

Visit	Screening/ Baseline	Random- isation	Treatment	Visit 2 3 months	Visit 3 6 months	Visit 4 12 months
Informed consent	x					
Randomisation		x				
Fitness for surgery assessment	x					
PSA	x			x	x	x
Standard care referral pathway to regional uro-oncology centre	x					
MRI guided pre-op surgical planning			x			
RARP (standard/control or NeuroSAFE/intervention)			x			
Adverse events			x	x		
EQ-5D-5L – (in clinic)	x			x	x	x
ICIQ – (in clinic)	x			x	x	x
IIEF – (in clinic)	x			x	x	x
RAND36 – (in clinic)	x			x	x	x
Additional Erectile function questionnaire				x	x	x
Adjuvant Treatments Assessment				x	x	x
Health Resource Diaries data collection				x	x	x

The study collected additional data through electronic PROMs, paper PROMs or telephone consultation at 2 years (RAND36, IIEF, EQ-5D-5L, ICIQ and Additional EF questionnaire), and at 3, 4 and 5 years via additional medical record review (EPIC-26, PSA & Adjuvant therapies) and telephone or clinic (BCR rates). These longer-term data are not covered in this SAP.

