4.5 Adverse events

The number and proportion of participants who experienced any adverse events and any serious adverse events within 90 days from surgery will be reported by arm (frequency and proportion).

A table will describe the type of SAE experienced. We will also report how many were considered possibly related to the NeuroSAFE intervention.

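### Non-serious adverse events recorded at the 6- and 12-month visits have no pre-specified by-arm table, because the SAP applies the protocol's 90-day limit for serious events to all adverse events.

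*SAP*

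**What the plan says.** Four places set the adverse event period, and they differ.

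- **Protocol 7.4 (Table of Assessments)** has the row "Adverse events x x x x x x x": screening, randomisation, treatment, 3 months, 6 months, 12 months and 2 years. The row does not separate serious from non-serious events.
- **Protocol 13.7.2** says that "the period of observation of serious adverse events extends from consent to 90 days post op". It gives two reasons: later serious events are unlikely to be related to surgery, and the limit spares the sites work. It makes one exception: "The trial will, however, continue to collect death SAEs throughout per section 13.7.1".
- **SAP 3.1** has the row "Adverse events x x", under treatment and Visit 2. Visits 3 and 4 are blank.
- **SAP 4.5** covers "any adverse events and any serious adverse events within 90 days from surgery will be reported by arm".

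SAP 2.1 sets the scope of the plan as the clinical analysis to Visit 4 (12 months). SAP 3.2 lists serious adverse events among the additional descriptive data and refers forward for detail. It does not name non-serious events.

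**The concern.** The protocol's 90-day limit concerns serious events, and its reasons are written for them. The SAP extends the limit to every adverse event and removes two scheduled collection points that fall within its own 12-month scope. It gives no reason for either step. If sites followed protocol 7.4, the database will hold non-serious events from Visits 3 and 4 that no named SAP table reports.

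What is at stake is the completeness of the safety description in an open-surgeon comparison of two operative techniques. The arms differ in more than the frozen section itself; in the NeuroSAFE arm "initial insertion of the robotic camera port is through a modified incision using the Alexis Laparoscopic System". Protocol section 3 says that the technique will be promoted throughout the NHS if it proves effective. A by-arm account of recorded adverse events over the whole 12 months is a modest requirement. If it is left to be decided after unblinding, the choice of what to show will no longer be pre-specified.

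**Working it through.** No sample size, power or event count enters this point. The check places the visits against day 90 and then reads the sections together.

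**1. Visit windows.** Inputs: visits at 3, 6 and 12 months, each ± 6 weeks (protocol 7.4). Conversion: 365.25 / 12 = 30.44 days per month; 6 weeks = 42 days.

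| Visit | Centre (days) | Protocol window (days) | Position relative to day 90 |
|---|---|---|---|
| Visit 2 | 3 × 30.44 = 91 | 49 to 133 | straddles |
| Visit 3 | 6 × 30.44 = 183 | 141 to 225 | wholly after |
| Visit 4 | 12 × 30.44 = 365 | 323 to 407 | wholly after |

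The wider windows in SAP 3.3 lead to the same result. Visit 3 at 4 to 12 months is days 122 to 365, and Visit 4 at 9 to 18 months is days 274 to 548. Both still lie wholly after day 90.

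**2. Share of follow-up.** 1 − 90 / 365.25 = 0.754. About 75% of the SAP's 12-month period has no named adverse event table.

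**3. Visit 2 does not match the 90-day limit exactly.** A Visit 2 held on day 49 leaves 90 − 49 = 41 days of the reporting period still to come. The next scheduled collection is Visit 3, which SAP 3.1 leaves blank. A Visit 2 held on day 133 can record an event that began after day 90, and that event is outside the SAP 4.5 table even though the SAP keeps the visit.

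**4. The sections side by side.**

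| Type of event | Protocol | SAP |
|---|---|---|
| Serious, to 90 days | observed (13.7.2) | by-arm table (4.5) |
| Serious, after 90 days | outside the observation period (13.7.2), although 7.4 still marks the visits | no table |
| Death, to 12 months | collected throughout (13.7.1, 13.7.2) | reported with reason (3.6.5) |
| Non-serious, to 90 days | scheduled (7.4) | by-arm table (4.5) |
| Non-serious, after 90 days to 12 months | scheduled at Visits 3 and 4 (7.4) | not in 3.1, not in 4.5 |

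The last row is the gap. For serious events the SAP follows the protocol's own rule. There the only inconsistency is inside the protocol, between the visit table and 13.7.2.

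**The case against.** **The SAP agrees with itself and with the protocol's 90-day rule.** For serious events this is right, and the 90-day window should stay. For non-serious events the protocol states no such rule, and 7.4 points the other way. The SAP may simply reflect what the sites did. If so, it should say so.

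**SAP 4.6 already covers it.** That section promises summaries of all study variables, by arm, at the different time points. It could be read to include later adverse events, so to say that they will certainly go unreported would be too strong. But it does not name adverse events, 4.5 is the section that does, and under SAP 3.1 there is no adverse event item at Visits 3 and 4 to summarise. The general clause does not clearly close the gap.

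**Stronger readings that a reader might infer.**

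- *Late incisional hernias or urethral strictures would be hidden.* Protocol 13.7 lists each at 2% ("incisional hernia (2"%), which is 202 × 0.02 = 4.04, or about four men per arm for each event. It places both under early post-operative events and gives no share presenting after 90 days. It also says that expected events need no adverse event form at any time, so a longer window would not by itself capture them. No passage says that late complications should differ by arm. The documents therefore support neither an estimate of missed cases nor separate rows for these events.
- *The 2-year visit is omitted.* Protocol 7.4 does mark it, but SAP 2.1 leaves longer-term outcomes to separate plans.
- *Events between consent and surgery are lost.* Protocol 13.7.2 starts at consent and SAP 4.5 at surgery. These events precede either operation, and the default analysis population (SAP 4.1.1) is the men operated on, so they hardly bear on the comparison of techniques.

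**Conclusion.** The concern holds in a limited form. Protocol 7.4, protocol 13.7.2, SAP 3.1 and SAP 4.5 disagree on the adverse event period. As a result, non-serious events recorded at Visits 3 and 4 have no pre-specified by-arm table.

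In time, the gap is about three quarters of the 12-month follow-up. In number of events, it cannot be sized from the documents. It affects descriptive safety reporting only and alters neither the primary outcome nor the three tested secondary outcomes.

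The conclusion assumes that adverse events were in fact collected at Visits 3 and 4 as protocol 7.4 schedules. If they were not, the discrepancy between the documents remains, but there would be little to tabulate.

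**What to change.** 1. Reconcile protocol 7.4, protocol 13.7.2, SAP 3.1 and SAP 4.5 so that each states the same collection period for serious and for non-serious events.
2. In SAP 3.1, mark adverse events at Visits 3 and 4, as in protocol 7.4. If collection stopped earlier in practice, state that and the reason.
3. In SAP 4.5, keep the 90-day table and keep 90 days as the serious-event window, with deaths handled as in protocol 13.7.2.
4. Add one descriptive by-arm table of any adverse event recorded after day 90 up to the 12-month visit, without tests. State whether events are placed by onset date or by recording date, and use the same rule in both tables so that each event appears once.
5. Label the added table as less completely captured. Note under both tables that the expected events in protocol 13.7 need no adverse event form and so are not reliably counted in either period.

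The cost is SAP wording and one more table from visits that the protocol already schedules. The downside is incomplete late capture: a sparse table could be misread as reassurance, which is why the label is needed.

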4.6 Descriptive statistics

We will provide summary statistics for all study variables, overall and by arm, at the different time points. Summary statistics for continuous variables will include mean, median, standard deviation range and/or interquartile range as appropriate. Categorical variables will be described using frequencies and percentages. Main variables (outcomes listed in section 3.2) will be described in the main report, while additional descriptive statistics will be reported in an appendix. Graphical representation may be considered.

The appendix will also report the frequency of missing data for all variables.

4.7 Primary outcome analysis

The primary estimand of interest will be the difference in mean IIEF-5 score at 12 months between participants allocated to the NeuroSAFE and those allocated to the standard treatment group among those who received the surgery.

The primary outcome (the IIEF-5 score at 12 month) will be analysed using a normal linear regression model. The model will include randomisation group, site (the stratification variable), age, and IIEF-5 at baseline. Continuous covariates (age and IIEF-5) will be included as a linear term, while site will be included as categorical. The estimated coefficient for the adjusted mean difference between randomisation groups will be presented alongside its 95% confidence interval and two-sided p-value

The primary analysis will include everyone in the mITT population with IIEF-5 available at 12 months.

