Outcomes and Analysis	
Primary outcome:
 
 
Comparison of the proportion of men who recover erectile function at 12-months according to allocated treatment arm (i.e. NeuroSAFE RARP [intervention] vs. standard RARP [control]). Erectile function is measured using the IIEF-5 questionnaire, where recovered function is defined as a score of 21 or more.
 
Pre-defined sub-group analysis: comparison of the proportion of men who recover erectile function at 12-months according to treatment arm, restricted to men who did not receive a pre-operative radiologist recommendation for bilateral nerve sparing.
 
 
For further sub-group analyses and sensitivity analyses, please see body of protocol, Outcomes Section.
 
Secondary outcomes:
 
There are 6 secondary outcomes:
 
 
1) Urinary Continence 
 
Comparison of the proportion of men who are continent at 3 months, measured using the ICIQ questionnaire, where continence is defined as a score of 5 or less between intervention and control arms.           
 
Additional subgroup analysis: restricted to men who did not receive a pre-operative radiologist recommendation for bilateral nerve sparing.
 
 
 
 
For further sub-group analyses and sensitivity analyses please see body of protocol, Outcomes Section.
 
 
2) Biochemical Recurrence (BCR)
 

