### 7.2 Outcome endpoints

#### 7.2.1 Primary

Comparison of the proportion of men who recover erectile function at 12 months allocated to the NeuroSAFE intervention versus the control arm. Erectile function is measured using the IIEF-5 patient reported outcome questionnaire, where recovered function is defined as a score of 21 or more.

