#### Verbal questionnaire responses (telephone)

- Since the Covid-19 Pandemic and government restrictions on movement including hospital appointments, the NeuroSAFE PROOF team have been conducting trial follow-up visits via telephone. All trial questionnaires have been sent to participants in the post. In order maintain data completeness on key outcome measures (such as erectile function at 12-months [IIEF-15] and urinary continence at 3 months [ICIQ]), the trial clinical team have been administering these PROM questionnaires over the telephone.

- As of protocol version 5.0, to ensure data completeness and to avoid submitting repeated protocol deviations for each instance, this method of data capture is now an accepted method of data collection. Any paper copies returned by post will supersede verbal responses.
- In order to distinguish between source data origins, a new electronic CRF database will have the facility to record whether PROM items were obtained by paper questionnaires submitted by post, electronic versions submitted following email reminders, or verbally with a clinician over the telephone.

Further planned analyses:

- Additional subgroup analysis: restricted to men who did not receive a pre-operative radiologist recommendation for bilateral nerve sparing.
- Additional subgroup analysis: patients who did not receive adjuvant treatment (adjuvant therapy defined as any additional treatment without a  $PSA > 0.2 \text{ ng/ml}$ ).
- Sensitivity analyses: additional analysis at 12 months
  - (a) IIEF-5 using a threshold  $\geq 15$
  - (b) IIEF-5 using a threshold of  $\geq 2$  for question 3
- Descriptive analysis of IIEF-5 at 3-, 6-, 12- and 24-months post-surgery

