## 12 STATISTICS

### 12.1 Sample size

As of protocol version 5.0, the NeuroSAFE sample size justification has been updated based on the analysis of 50 patients included in the NeuroSAFE PROOF Feasibility Trial, which was relevant to the original version of this protocol. 25 men were randomly allocated to NeuroSAFE RARP and 25 allocated to standard RARP. They were then followed up to 12-months following treatment. Outcomes related to these men will not be included in main trial analysis.

Based on analysis of the feasibility trial outcomes, the primary outcome was defined as a comparison of erectile function recovery at 12-months between men who underwent NeuroSAFE RARP (intervention) vs. standard RARP (control) with recovery defined as an IIEF-5 score of 21 or above.

The previous recruitment target according to protocol version 4.0 (August 2019) was for 404 men (364 evaluable). This sample size was calculated without the benefit of mature functional (i.e. PROMs/IIEF-15) results related to erectile function recovery.

A new sample size using the newly informed outcome data from the feasibility trial was prepared for protocol 5.0. The sample size is based on a 14% higher proportion of men with IIEF-5 score of 21 and above in the NeuroSAFE RARP (intervention) arm, compared to the control baseline proportion. At 90% power, an alpha of 0.05 and a loss to follow up of 10%, 416 patients (374 evaluable) would be the anticipated recruitment target. This sample size calculation is therefore deemed to be compatible with the sample size calculation submitted and used within protocol version 4.0 (August 2019). Furthermore, the iDMC reviewed the sample size assumptions on 16th Feb 2021 and were unblinded to results from the first 150 men recruited to the main trial. They advised the trial continue recruitment to the original number of 404 men (364 evaluable men). The iDMC will continue to review the recruitment target during the trial.

The secondary outcome #1, the proportion of men regaining continence at 3 months as defined by ICIQ score of 5 or less, is powered at 89% for a 15% increase in the NeuroSAFE RARP (intervention) arm compared to the standard RARP (control) arm at 3 months.

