### 12.2.1 Intent to treat population

The intent to treat (ITT) population, which is the primary population for efficacy, is defined as all men who provide written informed consent to receive the treatment.

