### 12.2.4 Statistical methods

Primary outcome: Comparison of the unpaired proportions of men who recover erectile function at 12 months allocated to the NeuroSAFE intervention versus the control arm, based on an IIEF-5 score of 21 or more. Statistical significance will be established using 95% confidence intervals calculated using the Wilson method. P-values will be reported. Further planned subgroup and sensitivity analyses will be conducted as detailed in section 7.2.1

The secondary outcome #1 will use similar methods to the primary outcome.

There will be no adjustment of p-values for secondary outcomes for multiple testing. STATA statistical software will be used.

Due to interruption the trial due to COVID pandemic, collection of outcomes at particular time points has been affected, with 3- and 6-month time points being less regimented than anticipated. Prior to data lock, the statistical methods will be

reviewed. It is possible that analysis could use survival analysis of time to event analysis up to 12 months for both analyses, if that would make better use of data from multiple time points.

Statistical methods will be reviewed on analysis of a sample of 20% of all data prior to data lock, after data collection and cleaning.

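### The protocol and the SAP name different primary endpoints, and no analysis in the available SAP text uses the protocol's endpoint (IIEF-5 of 21 or more at 12 months)

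*SAP*

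**What the plan says.** **Protocol v7.0.** Section 7.2.1 compares the proportions recovering erectile function at 12 months: "Erectile function is measured using the IIEF-5 patient reported outcome questionnaire, where recovered function is defined as a score of 21 or more". Section 12.2.4 gives the analysis, "Comparison of the unpaired proportions of men who recover erectile function at 12 months", with Wilson 95% confidence intervals and a p-value. Section 2 repeats the endpoint for a pre-defined subgroup: "comparison of the proportion of men who recover erectile function at 12-months according to treatment arm, restricted to men who did not receive" a radiologist's recommendation for bilateral nerve sparing. The threshold of 15 appears in 7.2.1 only under "Sensitivity analyses: additional analysis at 12 months". Section 12.1 states: "The sample size is based on a 14% higher proportion of men with IIEF-5 score of 21 and above".

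**SAP.** Section 3.2 lists the IIEF-5 score at 12 months as primary. Section 4.7 states: "The primary estimand of interest will be the difference in mean IIEF-5 score at 12 months", estimated by linear regression adjusted for site, age and baseline score. Section 4.10.3 uses the same model in men without a bilateral nerve-sparing recommendation (non-BNSR). Sections 3.6.1, 3.6.2 and 4.9.2 define binary recovery and time to recovery at 15 or more, both descriptive. The category table in 3.6.1 has a mild band of 17 to 21 and a no-dysfunction band of 22 to 25. A score of 21 or more appears only in the sample-size paragraph (1.4).

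**The concern.** The endpoint and the effect measure both change between the two documents, not just the model. A difference in means and a difference in the proportion reaching 21 answer different questions, and the same data can favour one and not the other. As the documents stand, a reader holding the protocol and a reader holding the SAP would look to different results to decide whether the trial succeeded.

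The protocol's endpoint also has no pre-specified place in the SAP. SAP 2.1 allows further secondary analyses after the planned ones. If 21 or more is reported by that route, it comes in as a later choice, although the current protocol calls it primary. The protocol's subgroup comparison is affected in the same way.

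**Working it through.** **1. Can the protocol's endpoint be recovered from the SAP's planned output?**

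| SAP item | Form of IIEF-5 | Gives 21 or more? |
|---|---|---|
| 4.7 primary | mean | no |
| 4.8 secondary | mean IIEF-6, mean ICIQ | no |
| 3.6.1 binary recovery | 15 or more | no |
| 3.6.2, 4.9.2 time to recovery | first score of 15 or more | no |
| 3.6.1 categories | 17–21 and 22–25 | no; gives n (%) at 22–25 only |
| 4.10.2, 4.10.3 interaction and subgroup | mean | no |
| 4.11 missing-data sensitivity | mean | no |

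Section 4.6 promises summaries of all study variables, but section 3 defines no variable at 21 or more. What is lost is narrow: men scoring exactly 21 cannot be separated from those scoring 17 to 20.

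**2. The SAP's sample size.** Inputs from SAP 1.4: 28% vs 42%, two-sided 5%, 80% power, 364 evaluable (182 per arm).

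- n per arm = {[1.960·√(2·0.35·0.65) + 0.842·√(0.28·0.72 + 0.42·0.58)] / 0.14}² = 181.02, rounded up to 182, so 364 in total.
- Power at 182 per arm = Φ{[0.14·√182 − 1.960·√0.455] / √0.4452} = Φ(0.849) = 80.2%.

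The SAP figure reproduces for 21 or more. Protocol 12.1 tells it differently. There, 364 evaluable is the v4.0 target, kept on the data monitoring committee's advice, and the v5.0 calculation for 21 or more gave 374 evaluable at 90% power. With the SAP's rates, 374 gives 81.3%, and 90% power needs 484.

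**3. What 182 per arm detects on the mean.** The documents give no SD or target difference.

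- Detectable difference at 80% power = (1.960 + 0.842)·√(2/182) = 0.294 SD, unadjusted.
- For an assumed SD of 6 to 9: 0.294 × 6 = 1.8 points to 0.294 × 9 = 2.6 points.

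**4. What the planned 14-point gain means for the mean.** Assumptions, none from the documents: bands 1–7, 8–20 and 21–25 with mean scores 4, 14 and 23, and controls split 50/22/28%. Power = Φ(d/SE − 1.96), with SE = √[(SD₀² + SD₁²)/182]. The ranges are without and with assumed within-band SDs of 2, 3.7 and 1.4.

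| Where the extra 14% come from | Mean difference | Power on the mean |
|---|---|---|
| all from the low band | 0.14 × 19 = 2.66 | 84–87% |
| both lower bands, in proportion 50:22 | 0.0972 × 19 + 0.0428 × 9 = 2.23 | 69–72% |
| both lower bands, equally | 0.07 × 19 + 0.07 × 9 = 1.96 | 57–60% |
| all from the middle band (extreme) | 0.14 × 9 = 1.26 | 27–29% |
| low-band men also reach the middle (30/28/42%) | −0.20 × 4 + 0.06 × 14 + 0.14 × 23 = 3.26 | 96–97% |
| normal shift taking 28% to 42% above the cut | 0.381 SD | 95% |

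Worked for the first row without spread: SDs 8.16 and 8.37, SE = √[(66.6 + 70.1)/182] = 0.866, power = Φ(2.66/0.866 − 1.96) = 86.7%.

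The first four rows were also varied: low band 40–60% of controls; band means 3–5, 12–16 and 22.5–24. Power is then 80–91% (low band), 46–78% (both bands) and 15–50% (middle band). The first four rows allow no gain below 21, which is unfavourable to a mean; the last two do allow it.

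**The case against.** The best defence is that this is a legitimate choice made in an orderly way. A mean uses the whole scale and is usually more precise than a cut-off when scores shift generally. The SAP makes the same move for continence: Protocol 7.2.2.1 uses ICIQ of 5 or less, and SAP 4.8 uses the mean. That looks like a general preference for continuous scores. Protocol 12.2 leaves the detail to a SAP locked before analysis, and 12.2.4 provides for a review of methods. SAP 2.3 requires approval and public posting before unblinding. The category table will show the proportion at 22 to 25, which matches the entry criterion for potency.

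Most of this stands. It shows that the mean can be defended and that the process has safeguards. It does not make the documents agree. The alternative that the protocol's review clause names is different: "It is possible that analysis could use survival analysis of time to event analysis up to 12 months for both analyses". A mean score is not mentioned there, and 22 or more is not 21 or more.

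A reader might infer more than the documents support:

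- *The switch was driven by results.* Nothing shows this. SAP 2.2 states that the two statisticians responsible for the SAP are blinded. It discloses an unblinded trial manager in an advisory role and one adviser with unblinded data on the first 120 participants. Disclosed access is not evidence of influence.
- *The change is undocumented.* The opening pages of the SAP were removed before review, so this cannot be known.
- *The trial is underpowered for the mean.* The range in step 4 runs both ways, and adjustment for covariates could raise power.
- *The 364 men were certainly sized on 21 or more.* SAP 1.4 says so; Protocol 12.1 gives a different history.

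**Conclusion.** The point holds as a conflict between the two documents, and it should be settled before unblinding. Protocol v7.0 makes the proportion with IIEF-5 of 21 or more primary, and the SAP makes the adjusted mean difference primary. No analysis in the available SAP text uses 21 or more, overall or in the subgroup. This part rests on the text alone and needs no assumption.

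The effect on power is indeterminate. The SAP's 364 evaluable men give 80.2% power for 28% vs 42% at 21 or more. For the mean, all that follows is a detectable difference of 0.294 SD. The range of about 15% to above 95% rests wholly on assumed score distributions, and the high end applies to a general shift in scores. It shows that the sample-size argument does not carry over automatically from one endpoint to the other, not that power is lost.

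**What to change.** Before unblinding:

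1. **Pre-specify 21 or more.** Add IIEF-5 of 21 or more at 12 months to SAP 3.2, 3.6.1 and 4.7 or 4.8, overall and in the non-BNSR subgroup. Report n (%) per arm and the risk difference with a Wilson-based 95% interval (Newcombe's form). For example, 76/182 vs 51/182 have Wilson limits of 34.8–49.0% and 22.0–34.9%. The difference is 13.7 points, with limits 0.137 − √(0.0692² + 0.0693²) = 3.9 points and 0.137 + √(0.0726² + 0.0602²) = 23.2 points. State its rank relative to the mean.
2. **Name one primary endpoint in both documents.** Record the date of and reason for the change, unless the removed SAP pages already do.
3. **If the mean stays primary,** say that SAP 1.4 derives 364 for 21 or more, and give the mean difference and assumed SD that 364 evaluable men can detect at 80% power.

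The cost is wording in two documents and one binary analysis in two populations, with no new data. The downside is one more comparison in each population, uncorrected because SAP 4.1.3 applies no multiplicity correction. A proportion is also less precise than a mean when the effect is a general shift. Both are reasons to fix the rank in advance.
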